c. Magnetic resonance spectroscopy (MRS): On the same or separate days, the participants will have MRS at 7Tesla at one point of time during which they will lie in the scanner while images of their brain will be recorded for one and half (1.5) hours. In the scanner the participants will be asked to be awake in the scanner, with head placed in a pad-cushioned coil. The volume coil $1H/^{31}P$ MRS imaging data will be acquired using the 7Tesla human MRI scanner at UT Southwestern Medical Center (UTSW). During the MRS data acquisition, subjects will be positioned head-first and supine in the MRI scanner, with the back of the head positioned to rest in the head coil. After preparatory imaging scans, which will be is mainly for localization and shimming, the ³¹P MRS data acquisition will be followed, which will include two surveying scans for evaluation of shimming quality on ³¹P spectra and of ³¹P excitation profiles along HF direction, then a six-slice 2D Chemical Shift Imaging(CSI) scan over the whole brain. For survey MRS scans, standard pulse-acquire technique will be used. Typical parameters are TR 4 s, sampling points 4 K, zero-filled to 8 K prior to FT, post-pulse delay 0.5 ms to filter out the broad phospholipids ³¹P signal. For CSI, slice-thickness will be 2 cm along LR direction, 4-6 slices, TR = 1 sec, NA = 4, sample points 2 K in-plane resolution 2x2cm², scan time ~45 min. After ³¹P MRSI data acquisition, voxel-by-voxel data analysis will be carried out to compare the regional difference in relative concentration of the phosphoryl metabolites; and all the measurements will be calculated from these values.

d. Sleep quality assessment (Figure 1, 2) SleepImage (MyCardio, LLC, Broomfield, CO) recorder collects data on electrocardiogram (ECG), actigraphy, body position, snore, ECG-derived respiration, HRV, HR. The SleepImage system includes a sleep recorder that is clinically validated and FDA cleared to allow the non-intrusive collection of objective measures of sleep quality. The participant will complete the sleep study for four (4) consecutive nights using the device along with self-assessment of sleep by answering the PSQI questionnaire for each night.

The sleep data will be analyzed by [name] and [name].

Figure 1: SleepImage sleep device in recording position.

[figure not shown]

Figure 2: SleepImage sleep device actual size.

Total time committed towards research will be around 37 hours excluding the time for transit.

Dental Intervention:

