Dental Intervention Risk: The minor physical risk associated with the sleep-monitoring aspects of this study are no more than those involved with standard tests of bodily (physiological) functions, for example wearing a heart monitor. The OA may cause pain in the jaw joint and teeth, and difficulty in opening or closing the jaw; these conditions are usually temporary. In the long term, the OA may cause changes in tooth position and in the bite (occlusion), as well as damage to the teeth and gums. We do not anticipate any significant physical risk from participating in this study. Though not impossible, we do not expect the adhesive hypoallergenic electrodes of the SleepImage device to cause itching or rashes. By wearing an OA, a subject may experience some discomfort and/or reduced function of the jaw joint (temporomandibular joint) and muscles of the jaw (chewing muscles) and of the face during and after treatment. Subjects may also experience some reduction in sleep quality due to discomfort while acclimating to wearing the OA. Other minor risks include temporary irritation of the mouth and oral cavity due to contact with the OA, and excessive salivation or dry mouth from mouth breathing. Repositioning of the lower jaw and tooth movement may also occur, but are typically minor and reversible. Also highly unlikely, a subject could swallow or aspirate part of an OA should it break. Participants will be carefully monitored for all of these risks by one or more of the study dentists. A telephone number and email address will be given to participants in case of questions and emergencies.

Data Storage: All data from questionnaires and cognitive tasks will be stored on a password-protected computer with the participant's study number. A master link linking participant numbers to names and other contact information will be stored on a different computer that is also password protected. All data will be stored without any identifying participant information linked to the data itself. All data will be stored without any identifying participant information – only the participant's study number will appear on the sample.

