Procedures to Maintain Confidentiality: We have taken a number of measures to ensure the confidentiality of the data and the safety of the participants. As we describe in the sections above, all data from the proposed study will be identified by a numerical ID code only. The information linking the numerical ID code to identifying information will be maintained separately and securely from the data themselves.

Every effort will be made to maintain the confidentiality of study records. Only the researchers will have access to any personally identifying information, that is, contact information for each participant (i.e., an email address or phone number). This information will not be stored with the participant data. An identification number will be assigned to each participant so that it will be possible to identify information to be shared with other researchers as described in the HIPAA. In data analysis, each participant will be identified by this number. All research materials with identifiable data, consisting of detailed health questionnaires, neuropsychological testing, and consent and HIPAA forms, will be kept in locked cabinets in the Center for BrainHealth at UTD. Imaging data at UTSW will be stored following HIPAA-compliant protocol. The data from the study may be published, but all information will be deidentified and HIPAA compliant. The confidentiality of the data will be maintained within the legal limits. Only associates listed on this study will have access to identifying data. The Research Coordinator, the Principal Investigator, and co-investigators will have access to the data and to the codes, along with designated research associates. The researchers will destroy the personal identifiers upon completion of data collection for the study.

9. Participant Safety and Data Safety Monitoring Plan

[name], PI will closely monitor the following at least on a monthly basis:

Study accrual rate Experience of study participants Study attrition including participant withdrawals/dropouts Patterns of AEs and/or unanticipated events Patterns of protocol deviations and/or violations Changes in risk/benefit

10. Potential Benefits

Benefit to participant:

The only benefit participant can have in this study is from dental intervention to improve sleep quality. Other benefits related to MRS and genetic data are not anticipated from this study.

Benefit to society:

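### The protocol does not mask spectroscopy processing to diagnostic group, or sleep analysis to group or visit, and the participant ID does not do so either

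*Combined protocol and SAP*

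**What the plan says.** Coding of participants is described in Section 8, under Data Storage and Procedures to Maintain Confidentiality.

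- **Purpose.** The confidentiality paragraph opens: "We have taken a number of measures to ensure the confidentiality of the data and the safety of the participants". The reason given for the number is data sharing: "An identification number will be assigned to each participant so that it will be possible to identify information to be shared with other researchers".
- **Use in analysis.** "In data analysis, each participant will be identified by this number".
- **What the key links.** "A master link linking participant numbers to names and other contact information will be stored on a different computer". Diagnosis and visit are not mentioned.
- **Who has access.** "The Research Coordinator, the Principal Investigator, and co-investigators will have access to the data and to the codes, along with designated research associates".

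The measurements themselves are described in Section 4.

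- **Section 4c (spectroscopy).** After acquisition, "voxel-by-voxel data analysis will be carried out to compare the regional difference" in metabolite concentrations, and all measurements derive from those values. Each participant is scanned once. No analyst is identified.
- **Section 4d (sleep).** "The sleep data will be analyzed by" two people, whose names are removed from the public text and whose roles are not given. Sleep is measured at baseline and again after the dental intervention.

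Neither section mentions masking, a reading rule, or a lock of values before group or visit is known.

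**The concern.** The metabolite ratios (ATP/PCr, Pi/PCr, PME/PDE) are the imaging measures for goals 1 and 3 in Section 1. The sleep quality index is the measure for goal 2 and the sleep outcome for goal 4. The protocol also states which way some of these should move: Section 2 treats a higher PME/PDE ratio as a sign of better brain health, and presents the appliance as a way to restore sleep quality.

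If someone who knows the group or visit chooses which voxels to keep, how to fit a spectrum, or which stretches of a recording to exclude, the values can drift in the expected direction. More participants would not remove that drift. In the group contrasts it would look like a disease difference. In goal 4 there is no comparison arm, so it would be added directly to the apparent appliance effect and could not be recovered afterwards.

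**Working it through.** **1. Does the ID mask group or visit?** Setting the Section 8 statements side by side:

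| Statement | What it conceals | Conceals group or visit? |
|---|---|---|
| Number used in analysis | Name | Not stated |
| Master link stored on another computer | Name, contact information | Not stated |
| Access to data and codes | Limits who can re-identify | Not stated |

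Nothing in Section 8 removes group or visit from an analysis file, and nothing in Sections 4c or 4d adds that protection. The documents do not say that the files show group or visit either. What they support is that the readings *can* be produced unmasked.

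**2. Which masking matters where?** Spectroscopy is done once, so only group is relevant. Sleep is recorded before and after the appliance, so both group and visit are relevant.

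**3. How much could it matter?** The plan gives no figure for measurement bias, so there is none to reproduce. For the setting I take 20 per group (Section 3) and alpha 0.055 (Section 6). As a check on that setting, 20 versus 20 with a 0.7 SD effect gives power 0.595 by the t-test and 0.616 by the normal approximation, close to the 0.60 quoted in Section 6.

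Assumptions not in the documents: a systematic shift of b SD with no change in variance; for pre/post, n pairs and correlation r. The true effect is zero, so every rejection is false.

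*Two groups of 20, two-sided.* Noncentrality = b × √(20/2); critical t on 38 df = 1.980.

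| b (SD) | Noncentrality | False-positive rate |
|---|---|---|
| 0 | 0 | 5.5% |
| 0.1 | 0.316 | 6.7% |
| 0.2 | 0.632 | 10.2% |
| 0.3 | 0.949 | 16.3% |

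*Pre/post, two-sided.* Standardised change dz = b / √(2(1 − r)); noncentrality = dz × √n; critical t = 2.204 for n = 10 (9 df) and 2.045 for n = 20 (19 df). At b = 0.3:

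| n | r | dz | Noncentrality | False-positive rate |
|---|---|---|---|---|
| 10 | 0.5 | 0.300 | 0.949 | 14.6% |
| 20 | 0.5 | 0.300 | 1.342 | 26.1% |
| 20 | 0.7 | 0.387 | 1.732 | 39.3% |
| 20 | 0.8 | 0.474 | 2.121 | 54.0% |

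For n = 20 and r = 0.7, smaller shifts of 0.1 and 0.2 SD give 9.2% and 20.7%. At b = 0 every row returns 5.5%.

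**The case against.** The strongest reply is that the shift may be negligible. Section 4d describes the sleep recorder as FDA cleared, clinically validated and a source of objective measures, and the documents do not say that an operator influences either the spectra or the sleep indices. A shift of zero fits the text as well as 0.3 SD does. This stands, and it is why the range starts at zero and the figures are only an illustration. The pre/post figures are weaker still, because the plan gives no Phase 2 sample size: entry depends on snoring, on the participant's choice and on the dentist's decision.

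A reader might infer more than the text supports in three ways.

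- *That the plan offers the ID as its protection against biased measurement.* It does not. The ID is presented only as a confidentiality measure, and the sentences about it are sound for that purpose.
- *That the analysts hold the key.* Section 8 gives the codes to "The Research Coordinator, the Principal Investigator, and co-investigators will have access to the data and to the codes" and to designated associates, but the sleep analysts' roles are not stated, no spectroscopy analyst is identified, and imaging is acquired at a different institution. The key is also largely beside the point, because as described it leads to names and not to diagnosis.
- *That pre/post bias touches the metabolite ratios.* They are measured once.

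A practical objection also stands. Baseline sleep results must be read and tied to the individual, because they decide who is offered the dental intervention (Sections 3 and 4). Locking all sleep indices before any linking would block that referral, so a blanket masking rule would not work.

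Finally, cognition is central to all four goals and the protocol states no masking for its testers either. That is true, but masked testers could need extra staff, whereas masked file processing does not.

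**Conclusion.** The concern holds as a gap in the planned conduct. The protocol states no masking of spectral processing to group, or of sleep analysis to group or visit, and the numerical ID does not supply it. It is not shown that the readings will be biased, or that any particular analyst will know group or visit.

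The size cannot be determined from the documents. For a group contrast of 20 versus 20, an assumed shift of 0 to 0.3 SD moves the false-positive rate from the nominal 5.5% to at most 16%. For the uncontrolled pre/post comparison, the 0.3 SD end of the range gives about 15% to 54% over 10 to 20 pairs and correlations of 0.5 to 0.8. The shift, the number of pairs and the correlation are all assumptions. If processing proves fully automated, the effect may be close to nil. The change is worth making because it is cheap and because a processing shift in goal 4 could not be separated out later.

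**What to change.** **Section 4c.** Add: *Before spectral processing, existing study staff relabel the MRS files with a random number that carries no group information. Metabolite ratios are locked under that number before diagnostic group is linked.*

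**Section 4d.** Leave the baseline sleep read-out used for dental referral unchanged, with the coordinator linking it to the participant. Add: *For the research analysis, the pre- and post-intervention recordings are processed together in one batch under random numbers that carry no group or visit information. Sleep indices are locked before group and visit are linked.*

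One further sentence in each section should say which steps are automated and which involve an operator's choice. That would let a reader judge how much the masking matters.

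**Cost.** One relabelling step by existing staff, and a second, batch pass of the baseline sleep files by the same analysts. No visit, sample size or clinical procedure changes.
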